4 INCLUSION CRITERIA

A. Shared Eligibility

1. Histologically and/or cytologically confirmed diagnosis of ER+ and/or PR+ breast cancer by local laboratory.
2. HER2-negative breast cancer defined as a negative in situ hybridization test or an IHC status of 0, 1+ or 2+. If IHC is 2+, a negative in situ hybridization (FISH, CISH, or SISH) test is required by local laboratory testing.
3. Patients are allowed (but not required) to have up to **two** lines of prior chemotherapy regimens in the metastatic setting for the dose expansion phase (). For the dose escalation cohort, up to three previous lines of chemotherapy in the metastatic setting is acceptable.
4. Measurable disease, i.e., at least one measurable lesion as per RECIST 1.1 criteria only **for expansion cohorts**.

5. For **escalation cohorts**, bone only disease is allowed. For expansion cohorts, there must be measurable disease as stated above (#4)..
6. ECOG PS 0 or 1.
7. Written informed consent must be obtained prior to any screening procedures and according to local guidelines.
8. Patient has adequate bone marrow and organ function as defined by the following laboratory values:
 - a. Absolute neutrophil count $\geq 1.5 \times 10^9/L$.
 - b. Platelets $\geq 100 \times 10^9/L$.
 - c. Hemoglobin $\geq 9 \text{ g/dL}$.
 - d. Potassium, total calcium (corrected for serum albumin), magnesium, and sodium within normal limits for the institution or corrected to within normal limits with supplements before first dose of study medication
 - e. INR ≤ 1.5 .
 - f. Serum creatinine $\leq 1.5 \times \text{ULN}$ or creatinine clearance $\geq 50 \text{ mL/min}$
 - g. In the absence of liver metastases, alanine aminotransferase (ALT) and aspartate aminotransferase (AST) $< 2.5 \times \text{ULN}$. If the patient has liver metastases, ALT and AST $< 5 \times \text{ULN}$.
 - h. Total bilirubin $\leq \text{ULN}$; or total bilirubin $\leq 3.0 \times \text{ULN}$ or direct bilirubin in patients with well-documented Gilbert's Syndrome
9. Must be able to swallow ribociclib and Tamoxifen capsules/tablets

B. Pre-menopausal Women Eligibility

1. Premenopausal women who received adjuvant Aromatase Inhibitor and Ovarian Suppression (AI + OS) in the adjuvant setting and completed at least 12 months of hormonal therapy.
2. Pre-menopausal women with *de novo* metastatic disease are eligible if they have had no prior endocrine therapy.
3. Premenopausal women who have not received Tamoxifen in the metastatic setting. Patients are allowed (but not required) to have up to **two** lines of prior chemotherapy regimens in the metastatic setting for the dose expansion phase. For the dose escalation cohort, up to three previous lines of chemotherapy in the metastatic setting is acceptable.

C. Post-menopausal Women and Men Eligibility

1. Postmenopausal women or men who have progressed on first-line or second line therapy with an aromatase inhibitor in the metastatic setting
2. Postmenopausal women or men who have recurred while on or after completion of adjuvant treatment with aromatase inhibitors (they have completed at least one year of AI in the adjuvant setting before progression on AI).
3. Postmenopausal women or men who are not considered candidates for treatment with an aromatase inhibitory by their oncologist, patients not willing to go on AI, or patients who were intolerant to AI.
10. Postmenopausal women or men are allowed (but not required) to have up to **two** lines of prior chemotherapy regimens in the metastatic setting for the dose expansion phase . For the dose escalation cohort, up to three previous lines of chemotherapy in the metastatic setting is acceptable.

5

EXCLUSION CRITERIA

1. Patients with inflammatory breast cancer.
2. Prior CDK4/6 inhibitor exposure.
3. Patient has received Tamoxifen in the metastatic setting (for more than 30 days) or has progressed while on Tamoxifen in the adjuvant setting.
4. Patient has a known hypersensitivity to ribociclib or excipients of tamoxifen..
5. Patient has a concurrent malignancy or malignancy within 3 years of starting study drug, with the exception of adequately treated, basal or squamous cell carcinoma, non-melanomatous skin cancer or curatively resected cervical cancer.
6. Patients with central nervous system (CNS) involvement unless they meet ALL of the following criteria:
 - a. At least 4 weeks from prior therapy completion (including radiation and/or surgery) to starting the study treatment
 - b. Clinically stable CNS tumor at the time of screening and not receiving steroids and/or enzyme-inducing anti-epileptic medications for brain metastases
7. Patient has impairment of gastrointestinal (GI) function or GI disease that may significantly alter the absorption of the study drugs (e.g., ulcerative diseases, uncontrolled nausea, vomiting, diarrhea, malabsorption syndrome, or small bowel resection).
8. Patient has a known history of HIV infection (testing not mandatory).
9. Patient has any other concurrent severe and/or uncontrolled medical condition that would, in the investigator's judgment, cause unacceptable safety risks, contraindicate patient participation in the clinical study or compromise compliance with the protocol (e.g. chronic pancreatitis, chronic active hepatitis, active untreated or uncontrolled fungal, bacterial or viral infections, etc.).
10. Clinically significant, uncontrolled heart disease and/or a recent events including any of the following:
 - a. History of acute coronary syndromes (including myocardial infarction, unstable angina, coronary artery bypass grafting, coronary angioplasty, or stenting) or symptomatic pericarditis within 12 months prior to screening.
 - b. History of documented congestive heart failure (New York Heart Association functional classification III-IV).
 - c. Documented cardiomyopathy.
 - d. Patient has a Left Ventricular Ejection Fraction (LVEF) < 50% as determined by Multiple Gated acquisition (MUGA) scan or echocardiogram (ECHO) at screening.
 - e. History of any cardiac arrhythmias, e.g., ventricular, supraventricular, nodal arrhythmias, conduction abnormality in the previous 12 months of screening.
 - f. Congenital long QT syndrome or family history of long QT syndrome
 - g. Sustained systolic blood pressure (SBP) >160 mmHg or <90 mmHg at screening. Must be corrected or controlled prior to starting study.
 - h. Bradycardia (heart rate <50 at rest) by ECG or pulse, at screening
 - i. On screening inability to determine the QTcF interval on the ECG (i.e.: unreadable or not interpretable) or QTcF > 450 msec (using Fridericia's correction). All as determined by screening ECG (mean of triplicate ECGs).
11. Patient is currently receiving any of the following medications and cannot be discontinued 7 days prior to starting study drug (see Table 7-5) :
 - a. Known strong inducers or inhibitors of CYP3A4/5, including grapefruit, grapefruit hybrids, pummelos, star-fruit, and Seville oranges.
 - b. That have a narrow therapeutic window and are predominantly metabolized through CYP3A4/5.

- c. That have a known risk to prolong the QT interval or induce Torsades de Pointes.
- d. Herbal preparations/medications, dietary supplements, not prescribed by an MD

12. Patient is currently receiving or has received systemic corticosteroids \leq 2 weeks prior to starting study drug, or who have not fully recovered from side effects of such treatment.
13. The following uses of corticosteroids are permitted: single doses, topical applications (e.g., for rash), inhaled sprays (e.g., for obstructive airways diseases), eye drops or local injections (e.g., intra-articular).
14. Patient is currently receiving warfarin or other coumarin-derived anticoagulant for treatment, prophylaxis or otherwise. Therapy with heparin, low molecular weight heparin (LMWH) or fondaparinux is allowed.
15. Participation in a prior investigational study within 30 days prior to enrollment
16. Patient who has received radiotherapy \leq 4 weeks or limited field radiation for palliation \leq 2 weeks prior to starting study drug, and who has not recovered to grade 1 or better from related side effects of such therapy (exceptions include alopecia) and/or in whom \geq 25% of the bone marrow was irradiated.
17. Patient has had major surgery within 14 days prior to starting study drug or has not recovered from major side effects (tumor biopsy is not considered as major surgery).
18. Patient has not recovered from all toxicities related to prior anticancer therapies to NCI-CTCAE version 4.03 Grade equal or less than one \leq 1 (Exception to this criterion: patients with any grade of alopecia are allowed to enter the study).
19. Patient with a Child-Pugh score B or C.
20. Patient has a history of non-compliance to medical regimen or inability to grant consent.
21. Pregnant or nursing (lactating) women, where pregnancy is defined as the state of a female after conception and until the termination of gestation, confirmed by a positive hCG laboratory test.]
22. Women of child-bearing potential, defined as all women physiologically capable of becoming pregnant, unless they are using highly effective methods of contraception throughout the study and for 12 weeks after study drug discontinuation. Highly effective contraception methods include:
 - a. Total abstinence when this is in line with the preferred and usual lifestyle of the patient. Periodic abstinence (e.g., calendar, ovulation, symptothermal, post-ovulation methods) and withdrawal are not acceptable methods of contraception.
 - b. Female sterilization (have had surgical bilateral oophorectomy with or without hysterectomy) or tubal ligation at least six weeks before taking study treatment. In case of tubal ligation alone, only when the reproductive status of the woman has been confirmed by follow up hormone level assessment.
 - c. Male sterilization (at least 6 months prior to screening). For female patients on the study, the vasectomized male partner should be the sole partner for that patient
 - d. No patients with HR+ disease should receive hormonal contraception, however the two following methods can be combined: Placement of an intrauterine device (IUD) or intrauterine system (IUS and barrier methods of contraception: Condom or Occlusive cap (diaphragm or cervical/vault caps) with spermicidal foam/gel/film/cream/ vaginal suppository.

Note: The use of oral contraception is not allowed.

Women are considered **post-menopausal** and not of child bearing potential if they have had 12 months of natural (spontaneous) amenorrhea with an appropriate clinical profile (e.g. age appropriate, history of vasomotor symptoms) or have had surgical bilateral oophorectomy (with or without hysterectomy) or tubal ligation at least six weeks ago. In the case of oophorectomy alone, only when the reproductive status of the woman has been confirmed by follow up hormone level assessment is she considered not of child bearing potential.]

- Patients who meet the eligibility criteria may be registered and enrolled on the trial. We will complete phase I portion of the study before proceeding to phase Ib expansion. At time of phase Ib expansion, we will alternate enrollment to both cohorts of our study, until both cohorts are complete.
- A signed copy of the institution's IRB-approved informed consent document must be placed on file.
- Patients must not start protocol treatment prior to registration.

7 TREATMENT PLAN:

Investigational Study Treatment

RIBOCICLIB will be supplied by Novartis or its designee in the form of 200 mg hard gelatin capsules/tablets as individual patient supply packaged in bottles.

All dosages prescribed and dispensed to the patient and all dose changes during the study must be recorded.

Dose and treatment schedule

Study treatment	Pharmaceutical form and route of administration	Dose	Frequency and/or Regimen
RIBOCICLIB	Capsules/tablets for oral use	400 mg	21 days on and 7 days off Or Daily (in continuous cohort)
RIBOCICLIB	Capsules/tablets for oral use	600 mg	21 days on and 7 days off

RIBOCICLIB will be administered as a flat-fixed dose (400 mg or 600 mg daily), and not by body weight or body surface area.

Patients must be instructed to return unused study drugs to the site at discontinuation or completion of treatment. Additionally, patients must be instructed to return empty bottles and/or any unused medication during their scheduled study visits to ensure compliance. The site personnel must ensure that the appropriate dose of each study drug is administered and that the drug accountability is performed.

In order to minimize the inter-patient variability of PK assessments, RIBOCICLIB should be taken as follows:

- Patients should be instructed to take the RIBOCICLIB capsules with a large glass of water (~250 ml) at the same time each morning.

- RIBOCICLIB can be taken without regard to meals; however, dietary habits around the time of dosing should be as consistent as possible throughout the study
- No major food effect on RIBOCICLIB exposure is expected. RIBOCICLIB is a high solubility (>30 mg/mL in physiological media), high permeability compound with a good dissolution profile at high doses, indicating that the exposure of RIBOCICLIB is not likely to be limited by solubility or dissolution.
- Patients should be instructed to swallow the RIBOCICLIB capsules whole and not to chew, crush or open them.
- If vomiting occurs during the course of treatment, no re-dosing of the patient is allowed before the next scheduled dose.
- Any doses that are missed (not taken within 6 hours of the intended time) should be skipped and should not be replaced or made up on a subsequent day.
- Patients must avoid consumption of grapefruit, Seville oranges or products containing the juice of each during the entire study and preferably 7 days before the first dose of study medications, due to potential CYP3A4 interaction with the study medications. Orange juice is allowed.

On days with PK, ECG sampling, chemistry panel and/or lipid panel sampling, the following additional guidelines should be followed:

- On a day when PK blood collection is scheduled at the clinic, patients must take study treatment in the clinic under the supervision of the Investigator or designee. On all other days patients may take the study treatment at home.
- On a day of chemistry panel and/or lipid panel sampling, patients must also take study treatment in the clinic under the supervision of the Investigator or designee. On all other days patients may take the study treatment at home.
- Pre-dose samples should be drawn prior to dosing. The sampling time of the PK samples and the dosing time must be precisely recorded in the CRF. Furthermore, the dosing date and time the study medication was taken on the day before the PK assessment must be precisely recorded in the CRF.
- Post-dose PK samples should be collected after dosing of the study treatment.
- A standard 12 lead ECG will be performed after the patient has been resting for 5-10 min prior to each time point indicated in study calendar. On cycle 1 day 1 (pre-dose), 3 ECG recordings must be taken at a minimum of 2-minute intervals. The combined QTcF values from these 3 ECGs will be averaged to provide a single baseline value for each patient. If an abnormal ECG is obtained at any time, patient's electrolytes must be reviewed and repeat ECG measurements must be done after correction of electrolyte abnormalities. In the event that a QTcF value of ≥ 501 ms is observed, a blood sample for PK will be collected to determine plasma levels of LEE011 and any other identified metabolites

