8 TREATMENT PLAN

Phase I/ Phase Ib dose expansion:

TAMOXIFEN: 20 mg PO daily will be given with RIBOCICLIB:

Ribociclib (LEE011)

In phase I: Ribociclib PO starting at a dose of 400 mg po for 21 days of a 28-day treatment cycle; this will be increased to 400 mg continuously. We will then evaluate 600 mg po daily for 21 days of a 28 day cycle if tolerated.

If there are no dose limiting toxicities, in the phase I portion, Tamoxifen 20 mg will be given with the MTD dose of Ribociclib in 15 patients. This is expected to be 600mg three weeks on and one week off. These patients will *not be stratified* for menopausal status.

If the 400mg continuous dose was well tolerated in the escalation arm, we will then expand this cohort in the phase Ib expansion, we will have an additional cohort of Tamoxifen 20 mg with 400 mg ribociclib in a continuous daily dose in an additional 15 patients. These patients will *not be stratified* for menopausal status.

Goserelin acetate (Zoladex) (3.6 mg subcutaneous every 28 days) will be given per NCCN guidelines to pre-menopausal and peri-menopausal. This will be given on day 1 of every cycle. We estimate that up to 20 of 40 patients on this protocol will require goserelin.

Goserelin is given if patient is premenopausal or peri-menopausal at the time of study entry.

Premenopausal status is defined as either:

- Patient had last menstrual period within the last 12 months.
- In case of therapy induced amenorrhea, with a plasma estradiol ≥ 10 pg/mL and/or FSH ≤ 40 IU/l or in the premenopausal range according to central laboratory definition.
- Patients who have undergone bilateral oophorectomy do not need goserelin.

Peri-menopausal status is defined as neither premenopausal nor postmenopausal (see exclusion criteria for definition).

8.1 Study Design:

Dose and Treatment Schedule – Table 8-1

No of pts	Cohort Level	RIBOCICLIB	Tamoxifen
3-6 (phase 1)	1	400 mg oral days 1-21, followed by 1 week break	20mg oral daily
3 -6 (phase 1)	2	400mg continuous	20 mg oral daily
3 -6 (phase 1)	3	600 mg oral day 1-21 followed by 1 week break	20 mg oral daily
15 (Ib dose expansion)	Phase Ib dose expansion	600 mg oral day 1-21 followed by 1 week break	20mg oral daily
15 (Ib dose	Phase Ib dose expansion-	400 mg oral daily	20 mg oral daily

expansion	continuous cohort	
------------------	--------------------------	--

Ribociclib Capsules/tablets for oral use 400 mg OR 600 mg Days 1-21 of each 28 day cycle or daily.

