8.2 Dosing regimen

- Ribociclib will be taken orally once daily on days 1-21 of each 28 day cycle. Days 22-28 will be a “rest” period from dosing with RIBOCICLIB.
- In the continuous cohort, 400 mg ribociclib will be taken daily (QD).
- Tamoxifen will be taken orally once daily on a continuous daily schedule (e.g. days 1-28 of each 28 day cycle) Goserelin will be given as an injectable subcutaneous implant on day 1 of every 28 day cycle. This will be given in pre and peri-menopausal women.

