8.5 STUDY CALENDAR

TESTS AND VISITS: Table 1-2

Test/ Study	Baseline ^c	C1 D1	C1 D8	C1 D15	C1 D22	C2 D1	C2 D22	C3 D1	C3 D15	C3 D16	C4 D1	C4 D22	C5 D1	C6 D1	C6 D22	C7 D1	C8 D1	C8 D22	C9 D1	C10 D1	C10 D22
Medical history	X																				
Vital Signs	X	X	X	X	X	X		X			X		X	X		X	X		X	X	
Child Pugh Score	X																				
Menopause status	X	X				X		X			X		X	X		X	X		X	X	
Physical exam	X	X	X	X	X	X		X			X		X	X		X	X		X	X	
Height	X																				
Weight	X	X				X		X			X		X	X		X	X		X	X	
Toxicity Assessment^a		X	X	X	X	X		X			X		X	X		X	X		X	X	
PK Samples^b									X	X											
Tumor Biopsy^d	X																				
CBC w/Diff	X	X	X	X	X	X		X			X		X	X		X	X		X	X	
CMP^j	X	X	X	X	X	X		X			X		X	X		X	X		X	X	
Lipid Panel	X										X							X			
PT & INR	X																				
Uric acid	X																				
FSH^k	X																				
LDH	X	X				X		X			X		X	X		X	X		X	X	
Biomarkers^e	X	X					X	X				X	X		X	X		X			X
Urinalysis	X	X				X		X			X		X	X		X	X		X	X	
Pregnancy Test^f	X																				
Staging Scans	X						X					X				X			X		X
2D Echo	X						X					X			X			X		X	
12 Lead EKGⁱ	X	X	X	X	X	X		X			X		X	X		X	X		X	X	
Disease assessment^h	X						X					X			X			X			X
Study Drug		X				X		X			X		X	X		X	X		X	X	

Dispensing																			
------------	--	--	--	--	--	--	--	--	--	--	--	--	--	--	--	--	--	--	--

Test/ Study	C11 D1	C12 D1	C12 D22	C13 D1	C14 D1	C15 D1	C15 D22	C16 D1	C17 D1	C18 D1	C18 D22	C19 D1	C20 D1	C21 D1	C21 D22	C22 D1	C23 D1	C24 D1	C24 D22	30 day F/U ^g
Medical history																				
Vital Signs	X	X		X	X	X		X	X	X		X	X	X		X	X	X		X
Menopause status	X	X		X	X	X		X	X	X		X	X	X		X	X	X		X
Physical exam	X	X		X	X	X		X	X	X		X	X	X		X	X	X		X
Height																				
Weight	X	X		X	X	X		X	X	X		X	X	X		X	X	X		X
Toxicity Assessment ^a	X	X		X	X	X		X	X	X		X	X	X		X	X	X		X
PK Samples ^b																				
Tumor Biopsy ^d																				X
CBC w/Diff	X	X		X	X	X		X	X	X		X	X	X		X	X	X		X
CMP ^j	X	X		X	X	X		X	X	X		X	X	X		X	X	X		X
Lipid Panel		X						X					X					X		
PT & INR																				
Uric acid																				
FSH ^k																				
LDH	X	X		X	X	X		X	X	X		X	X	X		X	X	X		X
Biomarkers ^e			X			X						X				X			X	X
Urinalysis	X	X		X	X	X		X	X	X		X	X	X		X	X	X		X
Pregnancy Test ^f																				
Scans			X				X				X				X				X	
2D Echo			X				X				X				X				X	
12 Lead EKG ⁱ	X	X		X	X	X		X	X	X		X	X	X		X	X	X		X
Disease assessment ^h			X			X					X				X				X	
Study Drug Dispensing	X	X		X	X	X		X	X	X		X	X	X		X	X	X		

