- a. Toxicity assessment must be performed until all treatment-related toxicities have been resolved or decreased to grade 1. Adverse events must be recorded up to 30 days after termination on study.
- b. PKs to be collected at C3D15 and C3D16 for steady state evaluation at 7 time points: Pre-dose, 0.5 hr post dose, 1 hr post dose, 2 Hrs post-dose, 4 Hrs Post dose, 8 hours post dose, 24 hours post dose.
- c. Tests done within 28 days can be used for baseline eligibility.
- d. Tumor Biopsy is optional. Baseline tumor biopsy for predictive markers (optional) if accessible, if not accessible based on surgical evaluation, then archival tissue from metastatic site allowed). Baseline tumor sample will be collected at screening, or following progression on prior treatment and prior to C1D1. A newly obtained post-progression tumor sample for resistance is optional. Should patient agree, it will be collected at time of progression and before a new treatment is initiated.
- e. Biomarkers to be collected include: CTC, CEA, Ca15-3, Ca 125, Ca 27-29/ (If clinically indicated) at time of restaging scans. Further biomarker testing for exploratory circulating tumor DNA will be collected predose on C1D1, predose C3D1, Predose C5D1, and C7D1. Biomarkers will also be collected at EOT, or within 15 days of the last dose.
- f. for women of childbearing potential. Pregnancy test will be repeated if clinically indicated.
- g. Thirty day follow up to occur after last dose of study drug. Used for either end of treatment or study completion. Includes resolution of serious adverse events and adverse events related to study treatment.
- h. Disease assessment is determined at visit every 8 weeks after staging scans and tumor marker collection
- i. EKG to be done in triplicate. Two minutes apart, after patient has been resting for 5-10 minutes
- j. Baseline CMP to include magnesium and phosphorous level for screening criteria.
- k. Female participants only

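### The only scheduled pregnancy test may be up to 28 days old at the first dose; require a negative hCG on Cycle 1 Day 1 or in the week before

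*Combined protocol and SAP*

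**What the plan says.** - **Exclusion.** Section 5, item 21 excludes "Pregnant or nursing (lactating) women, where pregnancy is defined as the state of a female after conception", to be confirmed by a positive hCG test. It gives no interval between the test and the first dose.
- **Schedule.** In the Section 8.5 calendar, the row "Pregnancy Test" is marked in the baseline column. No column from Cycle 1 Day 1 to the 30-day follow-up is marked.
- **Age of the test.** Footnote c: "Tests done within 28 days can be used for baseline eligibility". It does not say whether the 28 days run back from first dose, registration or another date.
- **Repeat.** Footnote f limits the row to women of child-bearing potential and adds: "Pregnancy test will be repeated if clinically indicated".
- **Contraception.** Item 22 excludes women of child-bearing potential unless they use highly effective contraception during the study and for 12 weeks after stopping study drug. Item 22d bars hormonal methods.
- **Ovarian suppression.** Section 8.2: "Goserelin will be given as an injectable subcutaneous implant on day 1 of every 28 day cycle", for pre- and peri-menopausal women.

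**The concern.** The plan treats exposure in pregnancy as a hazard. It excludes pregnant women, requires contraception for 12 weeks beyond the last dose, and has each pregnancy reported to the manufacturer within 24 hours (Section 12.2). The test that enforces the exclusion is nevertheless not tied to the start of treatment. A site that follows the plan exactly could give the first dose of ribociclib plus tamoxifen to a woman who conceived after her screening test.

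This looks like an omission. Several neighbouring criteria are tied to starting treatment: electrolytes must be normal before the first dose (Section 4, A.8d), blood pressure must be controlled before starting (item 10g), and items 12, 16 and 17 count back from the start of study drug. Item 21 is not tied in this way.

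What is at stake is the safety of individual patients. Sample size, error rates and the dose-escalation rule are not affected.

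**Working it through.** The plan states no figure to reproduce, so the check sets the provisions on one time line, with Cycle 1 Day 1 as day 0.

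**Inputs**
- Scheduled pregnancy tests: one, at baseline (Section 8.5).
- Oldest acceptable baseline test: 28 days (footnote c).
- Scheduled repeats before or on day 0: none (calendar row, footnote f).
- Women who are not postmenopausal: about 20 of 40 (Synopsis and Section 2.5).

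**Longest gap between the scheduled test and the first dose**
- If footnote c counts back from Cycle 1 Day 1: 0 − (−28) = 28 days.
- If it counts back from registration, and registration falls r days before day 0, the gap is 28 + r days. The documents do not give r. As an assumption, r from 0 to 7 gives 28 to 35 days. The first reading is the more lenient to the plan and is used from here on.
- With a 7-day window: at most 7 days, which is 28 − 7 = 21 days shorter.
- With the test on Cycle 1 Day 1: 0 days.

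**Number of women concerned**
The number of child-bearing potential is not given. The planning estimate of 20 of 40 (20/40 = 50%) covers all women who are not postmenopausal. It is therefore a ceiling, and only as good as that estimate.

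**What covers the gap at present**
- Contraception under item 22 lowers the chance of conception. It does not detect one.
- On Cycle 1 Day 1 the calendar has a menopause-status check and a physical examination. These can prompt a test under footnote f, but only if something raises suspicion.
- A missed period is not a reliable prompt. Section 8 classes some women without periods as premenopausal: "In case of therapy induced amenorrhea, with a plasma estradiol" or FSH in the stated range.
- Study-scheduled goserelin begins on day 1. A woman not already on ovarian suppression has none from this source between screening and the first dose.

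Each provision reduces the risk or may lead to a test. None requires a current negative result before dosing.

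**The case against.** The case for leaving the text alone has substance.

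- Item 21 carries no time limit, so a woman known to be pregnant is excluded whenever that becomes known before entry. It would be wrong to infer that the plan permits dosing in a recognised pregnancy. The gap concerns an unrecognised one.
- Item 22 admits only women already using highly effective contraception: abstinence, sterilisation, or an intrauterine device or system combined with a barrier method.
- Goserelin is described as standard of care outside the study (Synopsis), and one premenopausal group has had adjuvant ovarian suppression (Section 4, B.1). Some women may therefore be suppressed before day 1.
- Footnote c names no anchor, so 28 days at first dose is a reading of the text and not a stated rule.
- No document supports 7 days over another number, and a 7-day-old test still leaves a gap.

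These points stand as reasons for low priority. They do not put a test near the first dose. An unnamed anchor does not help the plan either, since counting from registration makes the gap longer.

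A reader might also infer a parallel safety gap for QTcF. Item 10i says of its 450 ms limit, "All as determined by screening ECG (mean of triplicate ECGs". Section 7 repeats the measurement before dosing, "On cycle 1 day 1 (pre-dose), 3 ECG recordings must be taken at a minimum of 2-minute intervals", but uses the average as a baseline value and states no limit for starting. That reading of the text is correct, but the documents do not support calling it a defect. Electrolytes must be normal before the first dose (A.8d), and drugs with known QT risk must be stopped 7 days earlier (item 11c). An abnormal ECG at any time leads to electrolyte review and a repeat after correction (Section 7). Section 7.2 requires no dose adjustment at 450–480 ms and interrupts from 481 ms, and the next ECG is on Day 8. Eligibility judged at screening, followed by on-treatment rules, is a coherent scheme. Re-applying 450 ms on day 1 is a debatable trade-off.

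Nor can it be said that a patient at 451–480 ms on day 1 has less margin than anyone who meets item 10i. That patient has met item 10i, because it is judged at screening. The margins to interruption (481 − 450 = 31 ms at the limit; 481 − 451 = 30 down to 481 − 480 = 1 ms in the band) are differences between thresholds. They do not show that anyone would cross 481 ms.

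**Conclusion.** The point holds for the timing of the pregnancy test. The plan allows a first dose up to 28 days after the only scheduled hCG test, with no repeat required. This assumes that the 28 days end on Cycle 1 Day 1 and that no clinical sign prompts a test.

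The chance of conception in that interval cannot be derived from the documents and should be low under item 22. At most about 20 of 40 patients could be concerned, and the true number of child-bearing potential is not given. The change is worth considering because it is cheap and protects patients, not because a frequent event is expected.

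How a pre-dose QTcF of 451–480 ms on Cycle 1 Day 1 is handled could be stated for clarity. That is optional and forms no part of this conclusion.

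**What to change.** In Section 8.5, exempt the pregnancy test from the 28-day allowance in footnote c. For women of child-bearing potential, require a negative hCG on Cycle 1 Day 1 or within the 7 days before it, with the result known before the first dose. State the same interval in item 21. The 7 days are a proposed window; testing on Cycle 1 Day 1 leaves the smallest gap and is preferable where the result can be had in time.

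The cost is amendment wording, one re-timed hCG test (or a second one when the baseline test is more than 7 days old), and an occasional delayed start.

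Optionally, the same amendment could add one sentence on how an averaged pre-dose Cycle 1 Day 1 QTcF of 451–480 ms is handled before the first dose.

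### The section 5 note makes tubal ligation alone a route to post-menopausal status, in conflict with section 8 and criterion 22b

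*Combined protocol and SAP*

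**What the plan says.** The note at the end of section 5 defines, in one sentence, who is post-menopausal and not of child-bearing potential. It gives three alternatives: 12 months of natural amenorrhea with a fitting clinical profile, bilateral oophorectomy, or tubal ligation. The surgical part reads "or have had surgical bilateral oophorectomy (with or without hysterectomy) or tubal ligation at least six weeks ago". The note then asks for hormone confirmation, but for the other operation: "In the case of oophorectomy alone, only when the reproductive status of the woman has been confirmed by follow up hormone level assessment".

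Criterion 22b, just above the note, lists sterilization among the contraceptive methods for women of child-bearing potential. It puts the confirmation on ligation: "In case of tubal ligation alone, only when the reproductive status of the woman has been confirmed by follow up hormone level assessment".

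Section 8 sets out who receives goserelin: "Goserelin is given if patient is premenopausal or peri-menopausal at the time of study entry". Its first premenopausal criterion is "Patient had last menstrual period within the last 12 months", with no exception for ligation, and the only operation it exempts from goserelin is bilateral oophorectomy. For the remaining class it refers back to section 5: "Peri-menopausal status is defined as neither premenopausal nor postmenopausal (see exclusion criteria for definition".

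The synopsis and section 2.5 give the standard criteria for a post-menopausal state as no cycles for more than 12 months and FSH of at least 40. Neither mentions ligation.

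**The concern.** Tubal ligation does not end ovarian function, yet the note makes it sufficient for post-menopausal status. Menopausal status decides whether section 4B or 4C applies. Child-bearing status decides whether study calendar note f requires the baseline pregnancy test and whether criterion 22 applies. If the note and the other texts classify the same woman differently, the site has no written rule for choosing between them. At stake are a consistent eligibility decision and a clear testing requirement for women with a ligation.

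**Working it through.** No arithmetic is involved. The check applies the written rules to one woman: last period within 12 months, ligation more than six weeks ago, no oophorectomy.

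**Menopausal class.** By the section 5 note she is post-menopausal through the ligation route. By section 8 she is premenopausal through her recent period. Section 8 takes its meaning of postmenopausal from section 5, so the two definitions are meant to work together, and here they give opposite answers.

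**Eligibility list.** Suppose also that she had no adjuvant aromatase inhibitor (AI) with ovarian suppression, did not progress on adjuvant tamoxifen, is unwilling to take an AI, and has had *d* days of tamoxifen in the metastatic setting. The relevant rules are:

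- B.1 requires adjuvant AI with ovarian suppression.
- B.2 requires de novo metastatic disease and no prior endocrine therapy.
- B.3 covers "Premenopausal women who have not received Tamoxifen in the metastatic setting".
- C.3 includes "patients not willing to go on AI, or patients who were intolerant to AI".
- Exclusion 3 bars more than 30 days of tamoxifen in the metastatic setting.

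| *d* | Exclusion 3 | List B | List C | Result |
|---|---|---|---|---|
| 0 | not triggered | B.3 met | C.3 met | eligible by either list |
| 1 to 30 | not triggered | B.1, B.2 and B.3 all failed | C.3 met | ineligible by B, eligible by C |
| more than 30 | triggered | – | – | ineligible by either list |

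The outcome changes only in the middle row. That row exists because B.3, read literally, allows no tamoxifen in the metastatic setting while exclusion 3 tolerates up to 30 days. If B.3 is read with the same tolerance, the woman is eligible by either list.

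**Pregnancy test and hormone confirmation.** The calendar schedules one pregnancy test, at baseline, and note f limits it to women of childbearing potential. Two readings are available:

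- If the note governs, she is outside that class. Note f does not require the test, and 22b, with its confirmation of hormone status, is never reached.
- If criterion 22 governs, the class is all women physiologically capable of becoming pregnant, and 22b lists ligation as a method that such women use. She is then inside the class, is tested, and needs the confirmation.

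The text does not say which reading takes precedence.

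**Goserelin.** She menstruates, so section 8 makes her premenopausal and she receives it. Her ligation does not exempt her.

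**The case against.** The strongest reply is that almost nothing follows from the conflict. Much of that reply stands.

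- A reader might infer that a ligation by itself turns an ineligible woman into an eligible one. It does not. The change also needs the mismatch between B.3 and exclusion 3, which affects premenopausal women with or without a ligation and would remain after this correction.
- A reader might infer that women with a ligation lose the baseline pregnancy test. The documents do not establish that. Criterion 22 and 22b support keeping them in the tested class, so the position is conflicting rather than lapsed. Exclusion 21 still bars any pregnant woman, note f allows repeat testing when clinically indicated, and FSH is drawn at baseline from all female participants.
- A reader might infer that menstruating women with a ligation would miss goserelin. Section 8 gives it to them. At the edge, a non-menstruating woman with a ligation (for example after hysterectomy with the ovaries kept) may not fit the written rule. The synopsis, however, treats goserelin as standard of care outside the study, and nothing bars its use.
- A reader might infer that the two hormone-confirmation sentences were simply swapped and that 22b is the correct one. The documents do not say which placement was intended. Hormone levels reflect ovarian function rather than tubal occlusion, so the note's placement may be deliberate.

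It can also be said that the study plans a single center, whose investigators would probably use clinical judgment. That lowers the practical risk but leaves the definition wrong: an operative eligibility text still calls a menstruating woman post-menopausal.

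**Conclusion.** The definition is wrong as written, and the matter is minor. The contradiction between the section 5 note and section 8 is direct and rests only on the current wording. Its consequences are an ambiguous choice between lists 4B and 4C and an unresolved conflict over the baseline pregnancy test and the 22b confirmation. The eligibility result differs only at 1 to 30 days of tamoxifen in the metastatic setting, assuming B.3 is read literally and the patient has the other features of the example. The number of such patients cannot be derived from the documents and is probably small.

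Nothing here reaches the statistical conclusions. Patients are not stratified by menopausal status, no planned analysis uses it, and the sample size and the rule of 8 or more responses are unchanged.

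**What to change.** Delete the words "or tubal ligation" from the post-menopausal definition in the section 5 note. Keep ligation only in 22b, as a contraceptive method with the hormone confirmation already written there. Women with a ligation who meet no other post-menopausal route then stay in the class that gets the baseline pregnancy test, and a menstruating woman with a ligation is premenopausal throughout.

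Do not move the note's hormone-confirmation sentence from oophorectomy to ligation. That sentence ends by declaring the woman not of child-bearing potential. Attached to ligation, it would restore the route just removed and contradict keeping these women in the tested class. It would also drop the confirmation for oophorectomy with no support in the documents.

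The change is wording only and adds no procedure, since the pregnancy test and baseline FSH are already in the calendar. The downside is a few extra pregnancy tests. The mismatch between B.3 and exclusion 3 needs its own correction.
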